## **STUDY ENDPOINTS**

The primary endpoints pertain to the main hypothesized outcome: namely, a significantly better-than-placebo mood response for escitalopram + celecoxib that is not related to altered pain perception.

The HAM-D rating scale (17 items from the 21-item scale) will be the main measure of clinical improvement. Onset of response is defined as the day of treatment when a 30% decline in the initial (day 0) HAM-D score is recorded and is maintained for two consecutive weeks. Treatment response is defined as a 50% reduction in the initial HAM-D score occurs. Symptom remission is defined as a HAM-D score of 7 or less.

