### **I. Primary Endpoint**

We seek to establish whether the combination therapy of escitalopram + celecoxib will augment antidepressant efficacy compared to escitalopram therapy alone as demonstrated by:

- a significantly earlier group response (earlier decline in HAM-D scores)
- a more robust group improvement in HAM-D scores at 8 weeks of treatment
- more patients with symptom remission than in the escitalopram + placebo group at 8 weeks

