## STUDY DESIGN

This is a 10-week, randomized, double-blind, two-arm, placebo-controlled study. The study includes a screening visit, a 1-week washout phase, a 1-week placebo run-in phase and an 8-week flexible dose phase. A minimum of 70 subjects will be randomized. The randomization code will be created and kept by the pharmacist in sealed envelopes for each individual subject. The PI will have access to the randomization code through the pharmacist if there is a medical safety issue.

At the screening visit, subjects will undergo a psychiatric interview. The diagnosis of Bipolar Depression (BPD) will be established in this examination using portions of the MINI. The study will be explained to all subjects. If a subject meets inclusion criteria, he or she will be asked to review the consent form and agree to participate. Subjects who meet the screening criteria and sign the IRB-approved consent form will undergo comprehensive assessments in order to quantify depression and associated symptoms.

At the end of the screening visit, subjects will be instructed how to taper the antidepressant they have been taking over the course of one week. A one-week taper is sufficient for all antidepressant medications except fluoxetine. Subjects taking fluoxetine will undergo a two-week taper/wash-out. After the taper, all subjects will return for a second visit to be placed on a 1-week single-blind placebo run-in. At the second screening visit, the subject will provide a saliva sample prior to undergoing assessments. Subjects will be instructed how to take pills (escitalopram placebo 10mg/day and celecoxib placebo 400mg/day) until the next visit one week later. Due to the fact that a one-week placebo run-in may be insufficient for some patients to reliably establish whether or not they are placebo responders, there will be an option to extend the placebo run-in for one additional week, at

the discretion of the PI. No increased risks are anticipated with the extension of the placebo phase, as patients are evaluated weekly and in close telephone contact.

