### II. Inclusion Criteria

- Male or female of any race and 18 - 65 years of age at time of screening visit.
- Diagnosis of BPD I or II (DSM-IV-TR (296.52, 296.53, 296.89) without significant co-morbid secondary medical or psychiatric diagnoses.

- Depressive symptoms that failed to remit in response to antidepressant therapy OR current breakthrough depressive episode in spite of being maintained on a mood stabilizer and/or an atypical antipsychotic agent.
- Managed mania/hypomania with a mood stabilizer other than lithium, or an atypical antipsychotic.
- A minimum score of 18 on the Hamilton Depression Scale (HAM-D), 17-item.
- Willingness to institute lights-out at 11:00pm hours on the nights before blood drawings.

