## STUDY TREATMENTS AND COMPLIANCE

Subjects who meet the eligibility criteria will receive one week of single-blinded escitalopram placebo + single-blinded celecoxib placebo. Subjects who continue to meet eligibility at randomization will receive open-label escitalopram (beginning at 10mg/day) + double-blinded treatment of celecoxib (fixed at 400mg/day) or placebo. Escitalopram doses may be optimized based on efficacy and tolerability over the 8 weeks of active treatment. Subjects will be randomized according to a fixed assignment ratio of 1:1 (escitalopram + celecoxib: escitalopram + placebo). Assignment to groups is based on a pharmacy generated randomization code.

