## STUDY PROCEDURES

### Schedule of Events

Procedure	Screen 1	Screen 2	Baseline	Week 1	Week 2	Week 4	Week 8
Consent	X						
Assign Subject ID	X						
MINI	X						
HAM-D/HAM-A/MADRS	X*	X*	X	X	X	X	X
CGI/CSSRS/AdverseEvents/CSULGIE	X		X	X	X	X	X
Self-Assessment Packet			X	X	X	X	X
Dispense Study Medication		PBO	X	X	X	X	X
Physical Exam	X						X
Drug Screen and Pregnancy Test	X						X
Routine Clinical Labs	X						X
Research Blood Draw			X			X	X
CBC/PT/PTT Monitoring	X				X	X	X
Pulse Wave Analysis			X			X	X

Heart Rate Variability			X			X
Albuterol Challenge			X			X
Pulse Wave Velocity			X			X
Saliva Sampling		X	X	X	X	X

\*HAM-D only.

Routine Clinical Labs include complete blood count, complete metabolic panel, lipid profile and thyroid function.

The following assessments are included in the self-assessment packet:

- Beck Depression Inventory (BDI)
- Beck Anxiety Inventory (BAI)
- State/Trait Anxiety Inventory (STAI)
- Spielberger Anger Expression Inventory (STAXI)
- International Physical Activity Questionnaire (I-PAQ)
- Quality of Life and Enjoyment Questionnaire (QLES-Q)
- The Short-Form McGill Pain Inventory (MPI)
- Perceived Stress Scale (PSS-14)

Subjects will be treated as outpatients for a total of ten weeks. Subjects must complete at least six weeks to be regarded as completers. If a subject chooses to withdraw from the study on or after six weeks of treatment, he or she will be asked to complete end-of-study assessments at that time. Those results will be carried forward for the purpose of data analysis.

Subjects will not receive any other type of therapeutic intervention (e.g., psychotherapy) during participation in the study. Such options may be offered to them at the conclusion of the study, if appropriate.

Subjects who complete the study and respond favorably will remain under the care of the LUMC physician, if they wish.

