## ASSESSMENTS

### I. Psychometric Data Collection Instruments

Mini International Neuropsychiatric Interview (MINI)

Hamilton Rating Scales for Depression (HAM-D) and Anxiety (HAM-A)

Beck Depression Inventory (BDI); Beck Anxiety Inventory (BAI)

MADRS-Montgomery Asberg Depression Rating Scale (MADRS)

Columbia Suicide Severity Rating Scale (C-SSRS)

State/Trait Anxiety Inventory (STAI)

Spielberger Anger Expression Inventory (STAXI)

Inventory of Clinically Significant Upper and Lower GI events (CSULGIE)

Short-Form McGill Pain Inventory (MPI)

Perceived Stress Scale (PSS-14)

Quality of Life and Enjoyment Questionnaire (QLES-Q)

International Physical Activity Questionnaire (IPAQ)

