## DATA ANALYSIS AND STATISTICAL METHODS

### I. Statistical Analysis

Specific Aim 1 is to determine if combined pharmacotherapy of escitalopram + celecoxib will result in earlier and/or improved affective responses compared to escitalopram + PBO. Additionally, Specific Aim 1 seeks to control for pain perception in this analysis. For this aim, the patients in the two treatment arms will be compared on HAM-D, HAM-A, MADRS, BDI, and BAI scores. This will be accomplished with an analysis of covariance conducted at weeks 1, 2, 4 and 8. Baseline mood scores and McGill Pain Inventory scores will be used as covariates. In addition, the number of patients who are and are not classified as remitters at week 8 (those having a HAM-D score of 7 or less) will be tallied and cross-referenced with treatment group (escitalopram + celecoxib or escitalopram + PBO). The frequencies in the resulting 2-by-2 contingency table will be analyzed with the Pearson Chi-Square Test for Association.

For Specific Aim 2, dealing with treatment safety and tolerability, the numbers of patients who do and do not experience adverse events at weeks 1, 2, 4, and 8 will be tallied and cross-referenced with treatment group. The frequencies in the resulting 2-by-2 contingency table will be analyzed with the Pearson Chi-Square Test for Association. Additionally, to understand whether any pharmacodynamic interaction exists between escitalopram and celecoxib, blood levels of escitalopram and celecoxib drawn at weeks 4 and 8 will be compared for patients in the two treatment groups with an analysis of covariance using baseline levels as a covariate. If there is no pharmacokinetic interaction then we expect that there will be no statistically significant results for these analyses.

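### No mania or hypomania rating is scheduled after the first screening visit, so a patient who switches polarity with a low HAM-D is counted as a remitter and switches are not systematically counted

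*Combined protocol and SAP*

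**What the plan says.** All references are to the combined protocol and SAP.

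- **Population and treatment.** Subjects have bipolar I or II disorder. Inclusion Criteria require "Managed mania/hypomania with a mood stabilizer other than lithium, or an atypical antipsychotic", with no scale or cut-off, and Target Population keeps that maintenance treatment in place throughout. Under Study Treatments and Compliance, all randomized subjects "will receive open-label escitalopram (beginning at 10mg/day) + double-blinded treatment of celecoxib (fixed at 400mg/day) or placebo".
- **Remission.** Study Endpoints: "Symptom remission is defined as a HAM-D score of 7 or less". Primary Endpoint lists "more patients with symptom remission than in the escitalopram + placebo group at 8 weeks" as one of three ways of showing benefit. Statistical Analysis tests it with a Pearson chi-square on that cut-off alone.
- **Mania assessment.** Study Design: "The diagnosis of Bipolar Depression (BPD) will be established in this examination using portions of the MINI". The Schedule of Events marks the MINI at Screen 1 only.
- **Post-baseline measures.** HAM-D, HAM-A and MADRS; the row "CGI/CSSRS/AdverseEvents/CSULGIE"; and a self-report packet on depression, anxiety, anger, activity, quality of life, pain and stress. None is described as a mania measure, and no bipolar version of the CGI is named.
- **Safety.** Specific Aim 2 concerns drug interaction, gastrointestinal bleeding and cardiovascular health. Its analysis tallies patients with and without adverse events, by arm, at each visit.
- **Late exits.** Study Design and Statistical Analysis carry the last observation forward for exits after Week 6; Study Design names termination as well as drop-out.

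**The concern.** In bipolar depression a patient can stop scoring as depressed by recovering or by moving into hypomania or mania. A depression scale with a cut-off of 7 is not built to tell these apart, and the remission rule has no second condition that would. The plan treats manic symptoms as relevant at entry, then schedules nothing that rates them while every subject takes an antidepressant.

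Two things are at stake. One part of the primary endpoint can credit an unfavourable outcome as a success. And the trial will have no defined, uniformly collected count of switches by arm, which readers of a bipolar antidepressant trial will want. Neither can be repaired after data collection: if mania was not rated at the visit, a low HAM-D cannot be reclassified reliably later.

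**Working it through.** **1. The plan's own figure.** Determination of Sample Size gives 45 per group for effect size 0.60, 80% power and alpha 0.05. Normal approximation: n = 2(1.96 + 0.8416)² / 0.60² = 43.6, so 44. The t-test version gives 44.6, so 45, with power 80.4%. The figure reproduces with a two-sided test and is not disputed. It rests on mean HAM-D at week 2, not on remission.

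**2. How a switch is classified.**

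| Situation at the last assessment | Under the stated rules |
|---|---|
| HAM-D 7 or less, euthymic | Remitter |
| HAM-D 7 or less, hypomanic, at week 8 | Remitter |
| HAM-D 7 or less, terminated for a switch after Week 6 | Carried forward as remitter |
| HAM-D above 7, hypomanic | Non-remitter |

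The second and third rows are the problem.

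**3. How many patients (assumption).** The documents give no switch rate, so a range is used. Expected switches per arm = 45 × risk:
- 2%: 0.9
- 5%: 2.25
- 10%: 4.5
- 15%: 6.75

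**4. Effect on the remission test (assumption).** Let true euthymic remission be 30% in both arms, and let every switched patient score 7 or less. Apparent remission is then 30% plus the switch rate.

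*Equal switching*, 5% in each arm: 35% v 35%. The difference stays zero and the test keeps its 5% level. Both reported rates are 5 points too high.

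*Unequal switching*, 5% on placebo, so p2 = 0.35. With n = 45 (√n = 6.708) and p̄ the mean of p1 and p2,

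P(reject) = Φ{ [ (p1 − p2)√n − 1.96√(2p̄(1 − p̄)) ] / √(p1(1 − p1) + p2(1 − p2)) }

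- 10% on celecoxib, p1 = 0.40: (0.3354 − 1.3419)/0.6837 = −1.472, giving 7.1%
- 15%, p1 = 0.45: (0.6708 − 1.3579)/0.6892 = −0.997, giving 15.9%
- 20%, p1 = 0.50: (1.0062 − 1.3702)/0.6910 = −0.527, giving 29.9%

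These are rejections in favour of celecoxib, a direction that holds 2.5% of the nominal 5%. The opposite tail matters only in the first case: (−0.3354 − 1.3419)/0.6837 = −2.453, or 0.7%, for a total of 7.8%. Exact binomial enumeration gives about 8%, 16% and 29%. With true remission of 20% or 40% instead of 30%, the formula gives 7.6%, 17.6% and 32.8%, or 6.9%, 15.5% and 29.4%.

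If only half of switched patients score 7 or less, the excess halves: 20% v 5% adds 7.5 points, not 15. If celecoxib reduced switching, the bias would run against it.

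**5. What measurement would deliver.** If no switch were seen in 45 rated patients, the one-sided 95% upper bound is 1 − 0.05^(1/45) = 6.4%. By the same formula, power to compare switch rates is about 14% for 10% v 5% ((0.3354 − 0.7301)/0.3708 = −1.064) and 58% for 20% v 5% ((1.0062 − 0.9167)/0.4555 = 0.196). The comparison would be descriptive.

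**The case against.** The plan is not blind to switching. Adverse Events Reporting covers all events, including those staff observe, with description, dates and intensity. Specific Aim 2 promises an inventory at each visit, and the exploratory endpoints mention a symptom checklist whose content is not shown and might include manic symptoms. Subjects are encouraged to report mental changes. The termination criteria let the investigator remove anyone with a condition that makes staying unsafe or inappropriate, so an overt switch may not reach week 8. Mood stabilizers or atypical antipsychotics continue in both arms. HAM-D items such as insomnia or agitation may hold some switched patients above 7. Escitalopram is common to both arms, and nothing in the documents suggests that celecoxib changes switching. Finally, remission is one of three primary components in a study that calls itself exploratory.

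Most of this stands and limits the point. A reader might infer that the safety data cannot show switching at all. That goes too far: reported or observed switches could be counted afterwards from the event descriptions. A reader might also infer that the remission comparison is biased, for instance that 5 points of switches would make up a quarter of a 30% v 50% contrast. That needs a one-sided excess, every such patient at 7 or less, and remission rates the documents do not give. Nor do the documents show that the MINI mania module was used at screening; they say only that portions were.

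What remains is not answered. No switch is defined, no instrument is named as measuring it, the Aim 2 tally does not separate it, and the remission rule ignores it. Safeguards that lower the risk do not measure it.

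**Conclusion.** The concern holds as a gap in measurement and endpoint definition, not as a demonstrated bias. Under the plan's rules a hypomanic patient with HAM-D of 7 or less is a remitter, including by carry-forward after Week 6, and any switch count would be unsystematic and probably too low.

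Its size depends on rates that the documents do not give. Assumed switch risks of 2% to 15% mean about 1 to 7 patients per arm of 45, of whom those scoring 7 or less are misclassified. The between-arm remission comparison is essentially unbiased if switching is equal, although both rates are inflated. With 10% to 20% switching on celecoxib against 5% on placebo, all scoring 7 or less, false rejection is roughly 7% to 30% instead of 5%. The upper end needs a fourfold difference that nothing in the documents predicts. The sample size and the week-2 mean HAM-D calculation are not challenged. The change is worth making because it is cheap and cannot be made afterwards.

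**What to change.** 1. Add a brief validated clinician mania rating, or the MINI mania/hypomania module, at Baseline and weeks 1, 2, 4 and 8, at any end-of-study assessment for early exits, and at both sites.
2. Define a switch in advance: instrument, threshold or diagnostic rule, and timing.
3. Define remission as HAM-D of 7 or less without a current manic or hypomanic episode. At minimum, prespecify this as a sensitivity analysis of the week 8 chi-square test that also covers subjects whose last observation is carried forward.
4. Report switches by arm in the safety analysis, as counts with exact confidence intervals and without a claim from the between-arm test.

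This concerns measurement and analysis only; clinical handling of a switch is for the investigators.

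Cost: probably a few minutes at each of five existing visits with the existing raters (an estimate; the documents give no timings), plus short wording changes in Study Endpoints, the Schedule of Events and Statistical Analysis. No extra patients are needed. The limitation to accept is low power for comparing switch rates, about 14% for 10% v 5%.

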### **I. Primary Endpoint**

We seek to establish whether the combination therapy of escitalopram + celecoxib will augment antidepressant efficacy compared to escitalopram therapy alone as demonstrated by:

- a significantly earlier group response (earlier decline in HAM-D scores)
- a more robust group improvement in HAM-D scores at 8 weeks of treatment
- more patients with symptom remission than in the escitalopram + placebo group at 8 weeks

## II. Secondary Endpoint

We seek to determine whether there is a reduction in pro-inflammatory biomarkers at end of treatment in patients randomized to receive the combination treatment. Three key pro-inflammatory biomarkers (TNFalpha, hsCRP and VEGF) shown to be robustly elevated in depressed patients will be measured. Baseline values will be compared to age and sex matched controls from a normative dataset of healthy subjects. We will also attempt to subtype BPD patients by a median split into two groups (high and very high) according to their baseline biomarker levels.

## III. Second Tier Exploratory Endpoints

Our “second tier endpoints” are exploratory in nature. Our study is not powered for them since existing data in the literature is insufficient to calculate an accurate sample size for these endpoints.

1. We will seek to establish whether a specific psychiatric symptom profile may be associated with the anticipated differential mood improvement in response to escitalopram + celecoxib or escitalopram + PBO. To that end, additional rating instruments have been included (over and above the HAM scales) and detailed assessments will be made of symptom profiles obtained from the rating instruments.
2. We will assess the safety and tolerability of the combination treatment by means of an adverse events symptom checklist and by relevant laboratory measures (e.g., CBC, PT, PTT).
3. Assessment of the efficacy of celecoxib by measuring PGE2 response to assess the extent of COX-2 inhibition.
4. An assessment of blood levels of escitalopram and celecoxib will tell us if these two agents interfere or promote each other's uptake and/or clearance.

## STUDY DESIGN

This is a 10-week, randomized, double-blind, two-arm, placebo-controlled study. The study includes a screening visit, a 1-week washout phase, a 1-week placebo run-in phase and an 8-week flexible dose phase. A minimum of 70 subjects will be randomized. The randomization code will be created and kept by the pharmacist in sealed envelopes for each individual subject. The PI will have access to the randomization code through the pharmacist if there is a medical safety issue.

At the screening visit, subjects will undergo a psychiatric interview. The diagnosis of Bipolar Depression (BPD) will be established in this examination using portions of the MINI. The study will be explained to all subjects. If a subject meets inclusion criteria, he or she will be asked to review the consent form and agree to participate. Subjects who meet the screening criteria and sign the IRB-approved consent form will undergo comprehensive assessments in order to quantify depression and associated symptoms.

At the end of the screening visit, subjects will be instructed how to taper the antidepressant they have been taking over the course of one week. A one-week taper is sufficient for all antidepressant medications except fluoxetine. Subjects taking fluoxetine will undergo a two-week taper/wash-out. After the taper, all subjects will return for a second visit to be placed on a 1-week single-blind placebo run-in. At the second screening visit, the subject will provide a saliva sample prior to undergoing assessments. Subjects will be instructed how to take pills (escitalopram placebo 10mg/day and celecoxib placebo 400mg/day) until the next visit one week later. Due to the fact that a one-week placebo run-in may be insufficient for some patients to reliably establish whether or not they are placebo responders, there will be an option to extend the placebo run-in for one additional week, at

the discretion of the PI. No increased risks are anticipated with the extension of the placebo phase, as patients are evaluated weekly and in close telephone contact.

At the Baseline visit, subjects will be reassessed for depression and associated symptoms. If subjects continue to score 18 or higher on the 17-item HAM-D scale, they will be randomized to receive escitalopram + celecoxib, or escitalopram + placebo in an assignment ratio 1:1. Subjects will then go on to complete assessments at Week 1, Week 2, Week 4 and Week 8. If the subject scores below 18 on the 17-item HAM-D scale at Baseline, he or she will be terminated from the study and classified as a placebo responder. At each of these visits, subjects will arrive 30 minutes before their scheduled appointment time, rest for 20 minutes in the exam room, and provide a saliva sample prior to undergoing any assessments. Terminated subjects will be offered conventional care at the same institution.

It is our desire to observe the diurnal nature of cortisol levels in saliva by measuring the patient's salivary cortisol levels at a time point prior to treatment and post treatment. At each of these two time points, we would collect saliva from the patient at five times during the day: upon awakening, approximately 30 minutes past awakening, before lunch, at approximately 3pm, and before bedtime. The patient would be required to do this at home and would then store the samples in their refrigerator until their next visit. Subjects will be provided with a log to record the exact time of saliva collection. We will be using salivettes purchased from Sarstedt Inc., and our Salivary Assay kits will be purchased from Salimetrics, LLC.

The overall study is powered for 90 subjects. We aim to randomize 70 subjects at LUMC. Approximately 30 subjects will be randomized by investigators at our sister site in Munich, Germany. At LUMC, 35 subjects will be randomized to each arm of the study. Subjects must complete 8 weeks of active medication to be considered study completers. We plan to enroll approximately 80 patients in anticipation of a 10% drop-out rate. The drop-out rate is based on our experience with our patient population over the past 5 years. If a subject drops out or is terminated after Week 6, their last observation will be carried forward in the analysis (LOCF). There are no healthy controls in this study because we already possess normative, untreated data for comparison.

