## VI. Criteria for Subject Termination

- Subject attempts suicide or seriously deteriorates; if so, appropriate care will be provided.
- Develops serious complications of an ulcer, such as gastrointestinal bleeding, perforation, or obstruction.
- Engages in behaviors or develops any condition that the PI deems makes it medically unsafe or inappropriate to remain in the study.

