All statistical analyses will be conducted using the latest version of SPSS software for Windows. If a subject drops out after completing 6 weeks on active medication (after randomization), we will use the last observation carried forward (LOCF method) to analyze the data. If a subject has completed at least one week on active medication after randomization, but drops out of the study at any time between week-1 and week-8, s/he will be included in the intent-to-treat analysis. Since this project seeks to provide proof-of-concept in bipolar depression, and is therefore exploratory in nature, we propose the tests of significance use a 0.05 alpha level. However, if this proposal develops further we may adjust our desired level of statistical significance to be in line with the number of tests so that the family wise Type I error rate could be held at 5%. This issue will be considered in the future.

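### A subject terminated for worsening after Week 6 can have the Week 4 HAM-D counted as the Week 8 outcome if no exit rating is taken

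*Combined protocol and SAP*

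**What the plan says.** The Study Design section sets the carry-forward rule and names terminated subjects alongside drop-outs: "If a subject drops out or is terminated after Week 6, their last observation will be carried forward in the analysis (LOCF"). The Statistical Analysis section has a similar rule that names drop-outs only: "If a subject drops out after completing 6 weeks on active medication (after randomization), we will use the last observation carried forward".

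On visits, the Study Design section says: "Subjects will then go on to complete assessments at Week 1, Week 2, Week 4 and Week 8". The row "HAM-D/HAM-A/MADRS" in the Schedule of Events table agrees. There is no Week 6 visit and no early-termination column.

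The text below that table adds an early final assessment, under this condition: "If a subject chooses to withdraw from the study on or after six weeks of treatment". The final ratings are then requested when the subject leaves, and it is these that are carried forward. Subjects removed by the investigator are not mentioned.

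The Criteria for Subject Termination include: "Subject attempts suicide or seriously deteriorates; if so, appropriate care will be provided". They also cover serious ulcer complications and anything the investigator judges unsafe or inappropriate. Separately, the section on benefits and risks has the investigator withdraw a patient who develops serious suicide risk.

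The Study Endpoints section defines remission by HAM-D alone. The planned Week 8 table uses "the number of patients who are and are not classified as remitters at week 8 (those having a HAM-D score of 7 or less"). No section makes an exception for a subject terminated because of worsening.

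**The concern.** Last observation carried forward assumes that the last score still describes the patient at Week 8. For someone removed because of a suicide attempt, serious deterioration or serious suicide risk, the reason for leaving contradicts that assumption. If the only available score predates the event, the analysis puts an earlier and possibly good score in place of a known bad course.

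Two of the three primary results are at stake: improvement in HAM-D at 8 weeks and the number of remitters at 8 weeks. The error would favour whichever arm had more late terminations of this kind. The documents do not suggest which arm that would be.

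**Working it through.** **Which score is carried forward**

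1. The rule applies after Week 6, to drop-outs and terminated subjects (Study Design).
2. The scheduled post-baseline HAM-D ratings are at Weeks 1, 2, 4 and 8. For a subject leaving in Week 7, the last scheduled rating is Week 4.
3. An exit rating replaces it for a subject who chooses to leave at or after six weeks (Schedule of Events). For a subject whom the investigator removes, the plan neither provides nor excludes one.
4. So for a subject terminated for worsening, either an exit HAM-D is taken and carried forward, or it is not and Week 4 is used. The plan does not settle which.
5. In either case no rule scores the event itself. A subject with a suicide attempt and an exit HAM-D of 7 or less would still be tallied as a remitter.

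Hypothetical case: HAM-D 22 at Baseline, 7 at Week 4, terminated for serious deterioration in Week 7, no exit rating. The rule gives a Week 8 HAM-D of 7, a 15-point improvement and a remission.

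**The plan's own figure**

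The plan's 45 per group (effect size 0.60, 80% power, alpha 0.05) reproduces. A two-sided two-sample t-test needs 44.6 per group, and power at 45 is 0.804. That calculation is for Week 2, so a rule that starts after Week 6 does not affect it.

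**How many subjects**

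The documents give a 10% drop-out rate, not split by time or reason. Assume that it applies to the 90 subjects and is spread evenly over 8 treatment weeks:

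- Leavers after Week 6: 90 × 0.10 × 2/8 = 2.25.
- Share leaving for worsening, assumed 10% to 50%: 2.25 × 0.10 = 0.2 to 2.25 × 0.50 = 1.1 subjects.
- Of these, share with Week 4 HAM-D of 7 or less, assumed 5% to 30%: 2.25 × 0.10 × 0.05 = 0.01 to 2.25 × 0.50 × 0.30 = 0.34 false remitters in the whole trial, if no exit ratings are taken.

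**What one subject does**

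- Remission: 1/45 = 2.2 percentage points in that arm.
- Mean HAM-D: carried at 7 when the true score is 18 to 30 (assumed), the raw arm mean is too low by (18 − 7)/45 = 0.24 to (30 − 7)/45 = 0.51 points.
- Pearson chi-square without continuity correction, 45 per arm, with assumed remitter counts and k subjects in the first arm re-scored as not remitted:

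| Assumed counts | k = 0 | k = 1 | k = 2 |
|---|---|---|---|
| 20 v 11 | 0.046 | 0.074 | 0.114 |
| 25 v 15 | 0.034 | 0.056 | 0.088 |
| 22 v 12 | 0.030 | 0.049 | 0.078 |
| 20 v 10 | 0.025 | 0.042 | 0.069 |

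These counts were chosen near the 0.05 boundary, where re-scoring one or two subjects for any reason changes the result. They show the scale of one subject's influence, not the likelihood of the problem.

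**The case against.** A reader might infer that the plan orders the Week 4 score to be used for every terminated subject. It does not. It says only that the last observation is used, and the one place that describes an assessment for a late leaver, the Schedule of Events section, carries forward the exit result. A site could reasonably apply that to terminated subjects as well. This stands, and it is why the point is conditional.

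A reader might also take the Safety Assessments section as proof that no HAM-D is done at termination, because it names only a physical examination and laboratory tests. That section would not be expected to list efficacy scales. Its timing, at enrollment and termination, matches the Screen 1 and Week 8 columns, so termination there may mean the final visit, where HAM-D is rated. It proves nothing either way.

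A third tempting reading is that any termination shows a failed outcome. An ulcer complication or another medical reason says nothing about whether the depression remitted, so the point is confined to suicide attempt, serious deterioration and serious suicide risk.

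Finally, the numbers are small and assumed. The 10% is stated with the plan to enroll about 80 subjects for 70 randomized at the US site, so it may include losses before randomization. The 90 are described as patients completing treatment, and leavers are to be replaced. The study also calls itself exploratory. All of this limits the weight of the point. It does not remove the gap in two primary results.

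**Conclusion.** The point holds in conditional form. Carry-forward expressly covers subjects terminated after Week 6, the exit assessment is written only for those who choose to leave, and no rule counts termination for worsening as failure. If no exit HAM-D is taken, a Week 4 score that predates the event can become the Week 8 result and can count as remission. The Study Design and Statistical Analysis sections also differ on whether terminated subjects are covered at all.

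The likely effect is small: 0.2 to 1.1 affected subjects in the HAM-D analysis and 0.01 to 0.34 false remitters. Both ranges rest on an evenly spread 10% drop-out, on assumed shares for reason and Week 4 score, and on no exit ratings being taken. The documents do not support a claim that the trial's conclusion would probably change. The change is still worth making, because it costs little and must be settled before the data are seen.

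**What to change.** 1. In the Schedule of Events section, reword the sentence that begins "If a subject chooses to withdraw from the study on or after six weeks of treatment" so that it covers any subject who withdraws or is terminated at or after six weeks. The end-of-study HAM-D is then sought from both groups and is the value carried forward. Make the rules in the Study Design and Statistical Analysis sections say the same, and name terminated subjects in both.
2. In the Week 8 remission table, count as not remitted any subject terminated for a suicide attempt or serious deterioration, or withdrawn for serious suicide risk. Subjects terminated for other medical reasons are classified by their exit HAM-D.
3. In the Week 8 HAM-D analysis, where a subject terminated or withdrawn for one of these worsening reasons has no exit rating, do not use the Week 4 score. Use the subject's own baseline HAM-D, meaning no improvement, so that the subject stays in the analysis. In the hypothetical case above this replaces 7 with 22, a change of 15/45 = 0.33 points in the raw arm mean.

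The cost is a few sentences and one additional use of a rating already in the study. No visit schedule, sample size or treatment rule changes. The remission rate may come out slightly less favourable, and some exit ratings may not be obtainable. Baseline substitution is a convention and will still understate the loss for a subject who ended worse than at baseline.
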